2.1.4 Exclusion criteria

Subjects will not be eligible to take part in the study if:

1. They have an ocular disorder which would normally contra-indicate contact lens wear.
2. They have a systemic disorder which would normally contra-indicate contact lens wear.
3. They are using any topical medication such as eye drops (including comfort drops) or ointment on a regular basis.
4. The spectacles they use for digital device viewing on the study have been made with specialist features for computer use, digital eye fatigue or are multifocal/bifocal.
5. They are aphakic.
6. They have had corneal refractive surgery.
7. They have any corneal distortion resulting from previous hard or rigid lens wear or have keratoconus.
8. They are pregnant or breastfeeding.
9. They have any infectious disease which would, in the opinion of the investigator, contraindicate contact lens wear or pose a risk to study personnel; or they have any immunosuppressive disease (e.g. HIV), or a history of anaphylaxis or severe allergic reaction.
10. They have evidence of a heterotropia or decompensating heterotropia on cover test.
11. They have a history of having been prescribed prism in their spectacles (by self report).

12. They have taken part in any other contact lens or care solution clinical trial or research, within two weeks prior to starting this study.

2.2 Subject discontinuation

In general, subjects should be discontinued at any time, if it is in their best interests, as judged by the investigator. Reasons for this may include clinical signs of grade 3 or more, lack of motivation, discomfort, repeated refusal to follow instructions or the use of non-study products such as solutions or lenses. Subjects will be discontinued if a serious adverse event occurs or if they miss two or more planned consecutive visits. Subjects who fail to satisfy all the inclusion and exclusion criteria will be discontinued and replaced. Subjects may choose to leave the study at their own request. All discontinuations will be carefully recorded.

2.3 Safety parameters, adverse events and concurrent illnesses

The key safety parameters are the serious and significant adverse events listed in Appendix A (adverse events are classified as 'serious', 'significant' or 'non-significant'). Clinical assessment is made at the study visit(s) for these parameters. The presence of any ocular adverse event will be recorded on the eCRF and reported to the Sponsor using CVI report forms, and those ocular adverse events described as 'serious' or 'significant' will be detailed in the final report. Similarly, any concurrent illness that is likely to impact on the relevance and quality of the captured data will be noted on the case report form.

2.3.1 Investigator obligations

At all times the investigator will act in the best interest of the subject. Referral or treatment of an adverse event or other clinical finding should be initiated in the best clinical judgement of the investigator, irrespective of the participation in the clinical study.

2.3.2 Reporting obligations

In the case of a 'serious' or 'significant' adverse ocular event, the Principal Investigator will notify the Industrial Contact Person as soon as possible. Manchester UREC and any regulatory authorities will be informed as required.

2.4 Study termination

If it becomes necessary to terminate the study earlier than planned, the Industrial Contact Person will notify the Principal Investigator who will end the study with the cooperation of other staff members. Manchester UREC will be informed.

2.5 Protocol deviations and device deficiencies

Any deviations from this protocol will be recorded, and reported to the Industrial Contact Person as appropriate. Manchester UREC will be informed as necessary. Device deficiencies will be recorded and reported to the Industrial Contact Person.

2.5.1 Protocol amendments

Any amendments will be agreed between the Industrial Contact Person and the Principal Investigator with the cooperation of other staff members. Amendments will be recorded, identified and distributed. Approval from Manchester UREC will be obtained as necessary.

2.6 Study resources

Study products will be stored according to the manufacturer’s product instructions.

2.6.1 Lenses

Details of the study lenses are provided in Table 2. The lens is CE marked. Initial lens selection will be as indicated by the manufacturer fitting guidelines.

| | |
|----------------------|---------------------------------|
| Name | Biofinity Energys |
| Manufacturer | CooperVision Inc. |
| Material | comfilcon A |
| EWC (%) | 48 |
| BOZR (mm) | 8.6 |
| Diameter (mm) | 14.0 |
| Spherical powers (D) | -0.50 to - 6.00 (0.25 steps) |

Table 2: Study lenses.

2.6.1.1 Use of lenses

Study contact lenses will be worn on a daily wear, re-useable basis. [REDACTED]

[REDACTED] The lenses will be disinfected and stored using PureMoist (Alcon Vision Care) and the use of comfort drops will not be allowed. The lenses are also to be worn for a minimum of 2 hours before attending the follow-up visits (CL group only).

2.6.2 Inventory control

All study lenses will be supplied by CooperVision Inc. All worn lenses will be discarded. Unworn lenses will be returned [REDACTED]

[REDACTED]
[REDACTED]
[REDACTED]
[REDACTED]

2.6.3 Clinical equipment

Clinical equipment is regularly maintained and calibrated as required. Standard operating procedures and international standards are used where appropriate.

2.7 Documentation

Documents related to this work that require archiving will be kept by Eurolens Research for a period of 20 years after completion of the final report. The Sponsor's permission will be sought before the documents are destroyed.

2.8 Data collection and analysis

Data collected in this work will be recorded on a custom developed database and an established data trail. Data handling will include export of the study information from the clinical database into spreadsheet format for manipulation, followed by export into a statistical package for analysis. Most clinical data will be entered directly onto the electronic case report form and is considered to be source data.

2.9 Study completion

The clinical phase of the study will be considered as complete when all subjects have signed the exit statement.

2.10 Confidentiality

All matters related to this work will remain confidential within Eurolens Research, the funding company and any regulatory authority (e.g. Manchester UREC). Eurolens Research will take all reasonable steps to ensure that specific lens-related information is not passed on to study participants unless this is required for clinical management of an adverse event. Personal subject information will not be made available. To cater for this, subjects will only be referred by their unique identity number in the study report. The data activities of Eurolens Research are registered with the data protection officer at The University of Manchester.

2.11 Study monitoring

In order to provide quality control and quality assurance as part of this work, the study monitor will:

1. Liaise closely with the Principal Investigator.
2. Monitor and ensure the safety of the subjects.
3. Ensure that the investigation is being conducted according to the protocol.

4. Monitor and review (or oversee review of) the study records to ensure accuracy.
5. Document their observations and make them available to relevant authorised parties (e.g. Manchester UREC).
6. Implement the Eurolens Research clinical monitoring standard operating procedure.

2.12 Clinical trial registration

This study will be registered with clinicaltrials.gov in accordance with section 801 of the Food and Drug Administration (FDA) Act which mandates the registration of certain clinical trials of drugs and medical devices.

Section 3. Subject management

3.1 Visit scheduling

Subjects will be required to attend up to four study visits (three, in the case of the spectacle group). Acceptable date ranges are shown in Table 3. Subjects in the contact lens group may need to attend for more than one 'teach' session.

| Visit | Target | Allowable range |
|------------------------------|----------------------------|-------------------------------|
| Initial visit | N/A | N/A |
| 2 week visit (CL group only) | 14 days from initial visit | 10-20 days from initial visit |
| 1 month visit | 30 days from initial visit | 25-35 days from initial visit |
| 2 month visit | 30 days from 1 month visit | 25-35 days from 1 month visit |

Table 3: Visits and allowable ranges.

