1.4 Study design

This will be a randomised, open label, parallel group study, in which 76 subjects will be randomised to either continue wearing their habitual spectacles, or the Biofinity Energys contact lens, for a period of two months.

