2.1.1 Subject withdrawal and replacement

This study includes up to four clinical visits. Once the study consent form is signed, the subject is considered to be enrolled on the study. Subjects who have signed the consent form, but who have not completed the dispensing visit will usually be replaced. All subject data will be included in the final analyses unless there are strong grounds for exclusion; such grounds will be detailed in the final report. At the end the study, all subjects will sign a study exit form.

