15. For those assigned to the contact lens group, the study lenses will be fitted and allowed to settle for five minutes or until tearing stops (whichever is the longer).

16. [REDACTED]
[REDACTED]
[REDACTED]
[REDACTED]

[REDACTED]

17. [REDACTED]

18. [REDACTED]

- I [REDACTED]
- I [REDACTED]
- I [REDACTED]

19. [REDACTED]

21. Subjects will be trained on contact lens application, removal, solution use and best practice immediately at the end of this visit or at a later date if required. More than one visit is possible for this 'teaching' session if they have problems with handling. Subjects will be dispensed with contact lenses and solution only once the Investigator is satisfied with their ability to successfully apply and remove the lenses.

22. Subjects will be discharged and asked to return for a two-week follow-up visit wearing the Biofinity Energys contact lenses, [REDACTED]

[REDACTED]

No formal 'building up' of wearing time will take place, [REDACTED]

[REDACTED]

Some subjects

may achieve this on the first day of wear, others may take a few days before they are happy to wear for 8 hours, but all subjects should progress to a minimum of 8 hours per day as soon as they are able. Subjects will also be asked to bring their lens case to the follow-up visit.

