3.2.3 Two-week visit (contact lens group only)

Subjects should attend wearing their Biofinity lenses which should have been in situ for at least 2 hours. Subjects who attend without lenses in situ for at least 2 hours will usually be rescheduled. The following procedures will be performed (any ocular measurement procedures outlined below will be carried out on each eye):

1. Any medical or ocular issues since the last visit will be recorded.

2. [Redacted]

3. [Redacted]

4. [Redacted]

5. The CVS-Q questionnaire will be completed.

6. [Redacted]

7. [Redacted]

■ [Redacted]

■ [Redacted]

■ [Redacted]

■ [Redacted]

■ [Redacted]

■ [Redacted]

■ [Redacted]

■ [Redacted]

■ [Redacted]

■ [Redacted]

■ [Redacted]

■ [Redacted]

8. [Redacted]

9. [Redacted]

- [REDACTED]
- [REDACTED]
- [REDACTED]
- [REDACTED]
10. [REDACTED]
- [REDACTED]
11. The study lenses will be removed and stored in PureMoist disinfecting solution.
12. A complete biomicroscopic examination will be conducted as outlined in Section 3.2.2 following which the lenses will can be re-applied (after rinsing with saline) or given back to the subject to take home.
13. The subject will be discharged and asked to return for the one month visit wearing the study lenses which need to have been worn for at least 2 hours. Subjects should be asked to wear their lenses for a minimum of 8 hours per day, 5 days per week, and whilst using digital devices for at least 4 hours per day.

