3.2.4 Visit 3: One month visit

For the contact lens group, subjects should attend wearing their Biofinity lenses which should have been in situ for at least 2 hours. Subjects who attend without lenses in situ for at least 2 hours will usually be rescheduled.

For the spectacle group, subjects should attend wearing (or having brought with them) the spectacles that they have been wearing for digital device use. Spectacles should have been worn for a minimum of 2 hours on the day of the visit.

For the contact lens group, this visit will be identical to the two week visit except that the contact lenses will be discarded at the end of the visit and they will be provided with a new pair of lenses.

For the spectacle group, the following will take place:

1. Any medical or ocular issues since the last visit will be recorded.
2. Spectacle wearing times since the previous visit will be recorded (hours per day, days per week and comfortable hours per day).
3. [REDACTED]
4. [REDACTED]
5. The CVS-Q questionnaire will be completed.
6. [REDACTED]

7. [REDACTED]
8. The subject will be discharged and asked to return for the two month visit wearing their spectacles. Subjects should be asked to wear their spectacles for a minimum of eight hours per day, five days per week, and whilst using digital devices for at least four hours per day.

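### Should the contact lens visits be timed from lens dispensing rather than from the initial visit?

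*Combined protocol and SAP*

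**What the plan says.** Table 3 in section 3.1 gives the two-week visit, attended by the contact lens group only, a target of "14 days from initial visit" and a window of "10-20 days from initial visit". The one-month visit is due on day 30 (window 25 to 35), also counted from the initial visit. The two-month visit is due 30 days (25 to 35) after the one-month visit. The last two rows apply to both arms.

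In section 3.2.2, randomisation is step 14 of the initial visit. Step 21 then has contact lens subjects trained "immediately at the end of this visit or at a later date if required", possibly over several sessions, and adds: "Subjects will be dispensed with contact lenses and solution only once the Investigator is satisfied with their ability". Section 3.1 itself mentions, just above or beside Table 3, that extra teaching sessions may be needed.

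Four other places bear on the point:
- Section 1.4 has subjects use their spectacles "or the Biofinity Energys contact lens, for a period of two months".
- Section 3.2.3 says "Subjects who attend without lenses in situ for at least 2 hours will usually be rescheduled".
- Section 2.1.1 says that consented subjects "who have not completed the dispensing visit will usually be replaced".
- Section 3.2.4 says that at one month "the contact lenses will be discarded at the end of the visit and they will be provided with a new pair of lenses".

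**The concern.** Wear at home begins when lenses are dispensed, but the visit clock starts at the initial visit. Inclusion criterion 4 restricts the trial to people new to contact lenses, so some handling difficulty is foreseeable. The visible text puts no limit on how long dispensing may be delayed, and it does not restart the clock at dispensing.

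If dispensing is late, a CVS-Q score labelled two-week, one-month or two-month follows less wear than its label says. The two-week score could fall within early adaptation, since step 22 accepts that some subjects need a few days to reach 8 hours of wear. A site that waits for a fair amount of wear may instead push the two-week visit outside its window. A reader of the report who is not given the dispensing date could see neither effect. Section 2.1.1 also refers to a dispensing visit, which has no row of its own in Table 3.

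**Working it through.** **Inputs.** Visit targets and windows come from Table 3. The delay d is the number of days from the initial visit to dispensing. The documents do not give it, so the values 3, 7 and 10 below are assumptions.

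**Formula.** Days since dispensing at a visit = visit day counted from the initial visit, minus d.

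**No delay (the plan's own figures).** The targets are 14, 30 and 30 + 30 = 60 days. The windows are 10-20, 25-35, and 25 + 25 = 50 to 35 + 35 = 70 days. These match the labels.

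**With a delay.** The two-month visit carries the same shortfall because it is chained to the one-month visit.

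| d | Two-week: target (window) | One-month: target (window) | Two-month: target (window) |
|---|---|---|---|
| 0 | 14 (10-20) | 30 (25-35) | 60 (50-70) |
| 3 | 11 (7-17) | 27 (22-32) | 57 (47-67) |
| 7 | 7 (3-13) | 23 (18-28) | 53 (43-63) |
| 10 | 4 (0-10) | 20 (15-25) | 50 (40-60) |

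For d = 7 the loss at target is 7/14 = 50%, 7/30 = 23% and 7/60 = 12%.

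**When the labelled wear becomes unreachable in window.**
- Two-week: 20 - d < 14, so d > 6.
- One-month: 35 - d < 30, so d > 5.
- Two-month: 70 - d < 60, so d > 10.

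Up to those delays a late visit inside the window can make up the full shortfall. At the two-month visit, a subject seen on target dates has 60 - d days of wear. That is at least 50 for any d up to 10, and 50 days is the least that Table 3 already accepts with no delay.

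**If the site moves the two-week visit to 14 days after dispensing.** It falls on day 14 + d. That is past day 20 from d = 7, and reaches the one-month window (day 25) from d = 11. With d above 20 the two-week window closes before dispensing, so the window and the 2-hour wear rule could not both be met.

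**The alternative anchor.** Timing the two-week and one-month visits from dispensing would give 14, 30 and 60 days of wear at target for any d. Time since randomisation at the two shared visits would then be 30 + d and 60 + d days in the lens arm, against 30 and 60 in the spectacle arm. The mismatch of d days moves from exposure to the between-arm comparison.

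**The case for a change.** The best argument for a change is that it is cheap and that the protocol foresees the cause. A footnote to Table 3, one recorded date and two descriptive lines in the report would align each label with actual wear and avoid out-of-window two-week visits caused by the protocol's own teaching rule. On target dates, a late-dispensed subject does not get the two months in section 1.4. The comparator is unchanged spectacle wear, so unequal time since randomisation might be thought harmless.

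Part of this stands. The labels overstate wear for late-dispensed subjects seen on target dates, and days from dispensing would be a useful descriptive line.

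The case for re-anchoring is weaker:
- The clock for the lens arm would depend on an event after randomisation. It could not be set for a subject still in training on day 25, when nobody yet knows whether that subject will be dispensed.
- The two-week visit has no spectacle counterpart, so mistiming it cannot bias a between-arm comparison at that visit.
- At the final visit the lenses in use were issued at one month and are 25 to 35 days old whatever the delay.
- Section 2.5 has deviations recorded, which covers out-of-window visits. Section 3.1.1 has investigator-instructed visits outside the schedule entered in the database, which arguably covers later teaching sessions.
- Lines around steps 21 and 22 and in section 2.6.2 are redacted. A limit on the delay or a dispensing record may be there, so neither can be called absent.

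The wording in section 2.1.1 is minor. That section speaks of all subjects and of up to four visits, and Table 3 lists exactly four, so the dispensing visit is most naturally the initial visit under another name. If it means actual dispensing instead, the usual replacement of such subjects would limit the extreme delays.

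**Conclusion.** No change to the plan follows. Table 3 does count from the initial visit while dispensing may come later, and at target dates wear falls short by exactly the delay. That is the price of a defensible choice: counting from the visit at which subjects are randomised assesses both arms at the same time since randomisation. Counting from dispensing would buy accurate wear labels by giving that up, and statisticians could reasonably differ on which to prefer.

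The size is modest for short delays. A delay of 3 days leaves 11, 27 and 57 days of wear at target. The labelled wear remains reachable in window up to delays of 6, 5 and 10 days. The picture worsens only with delays of about a week or more, and the documents do not say how often, if ever, those occur. The effect on CVS-Q cannot be derived from the documents; judging it small is an opinion, resting on short delays and on the two-week visit having no comparator.

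An analyst who holds the dispensing dates can report days from dispensing to each CVS-Q for the lens group without amending the schedule. That would add detail to the report and leave the between-arm result as it is. The dispensing-visit wording in section 2.1.1 is a clerical matter to tidy if the text is reopened.

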3.1.1 Unscheduled visits

Subjects who attend at their own volition, (or as instructed to do so by the investigator) rather than for a scheduled study visit, will be examined and the visit will be classified as 'unscheduled'. Data collected at these visits will be recorded on the clinical study database.

3.1.2 Missed visits

Subjects not attending for a visit will be contacted and encouraged to return for assessment. If two consecutive study visits are missed, the subject will be discontinued. It is expected that Eurolens Research personnel will attempt all reasonable means of communication in this event, including corresponding with the subject by letter.

3.2 Visit conduct

3.2.1 Pre-enrolment

The subject will receive a study-specific information form outlining the study at least 24 hours before the initial visit.

At a suitable time, each subject will be asked to watch a short on-line information presentation detailing study visits and procedures. They will be asked to complete several multiple-choice questions to gauge their understanding of the study. Upon successful completion of these questions, the subject will be booked to attend the initial visit.

3.2.2 Initial visit

Subjects should attend this visit wearing (or having brought along) the spectacles that they use for digital device use (the visit cannot go ahead if they do not bring their spectacles). They will then be required to sign an informed consent form prior to

enrolment [REDACTED] A copy of the signed form will be issued to the subject. When the subject has signed the consent form, they are considered to be enrolled on the study.

Subjects will be instructed on the following:

- Lens handling, application and removal, where necessary.
- Use of multipurpose care regimen, where necessary.
- Specific study instructions, such as the importance of not using any other contact lens products.
- General information such as the management of red eyes.

The following procedures will be performed (any ocular measurement procedures outlined below will be carried out on each eye):

1. Details of the ocular history of the subject will be noted (including habitual spectacle details and wear time) This will include recording details about the spectacles to ensure the same pair are worn for the entire study.
2. Details of general health and medications will be recorded.
3. [REDACTED]
4. The CVS-Q questionnaire will be completed.
5. [REDACTED]
6. The BVD of the subject's spectacles will be recorded by asking the subject to position the spectacles on their own face (if not already being worn).
7. Focimetry will be carried out on the subject's spectacles to ascertain the prescription of the lenses.
8. [REDACTED]
[REDACTED]
[REDACTED]
[REDACTED]
[REDACTED]
9. [REDACTED]
[REDACTED]
[REDACTED]
10. [REDACTED]
[REDACTED]
11. [REDACTED]
[REDACTED]
[REDACTED]
[REDACTED]

- [REDACTED]
- [REDACTED]

12. [REDACTED]
[REDACTED]
[REDACTED]
[REDACTED]
[REDACTED]
[REDACTED]
[REDACTED]

[REDACTED]

The presence of any ocular adverse events will be recorded [REDACTED]

13. The investigator will confirm that the subject satisfies all the inclusion and exclusion criteria. Subjects who fail to meet all the criteria at this time will usually be discontinued and replaced. If in the opinion of the investigator, the subject may be eligible at a later date, the subject may be brought back for up to ONE repeat visit of this type.

14. The subject will be randomised to one of the two treatment groups. The spectacle wearers will be discharged from the study visit at this point, and asked to return for the one-month visit. [REDACTED]

[REDACTED]
[REDACTED]
[REDACTED]

15. For those assigned to the contact lens group, the study lenses will be fitted and allowed to settle for five minutes or until tearing stops (whichever is the longer).

16. [REDACTED]
[REDACTED]
[REDACTED]
[REDACTED]

[REDACTED]

17. [REDACTED]

18. [REDACTED]

- I [REDACTED]
- I [REDACTED]
- I [REDACTED]

19. [REDACTED]

21. Subjects will be trained on contact lens application, removal, solution use and best practice immediately at the end of this visit or at a later date if required. More than one visit is possible for this 'teaching' session if they have problems with handling. Subjects will be dispensed with contact lenses and solution only once the Investigator is satisfied with their ability to successfully apply and remove the lenses.

22. Subjects will be discharged and asked to return for a two-week follow-up visit wearing the Biofinity Energys contact lenses, [REDACTED]

[REDACTED]

No formal 'building up' of wearing time will take place, [REDACTED]

[REDACTED]

Some subjects

may achieve this on the first day of wear, others may take a few days before they are happy to wear for 8 hours, but all subjects should progress to a minimum of 8 hours per day as soon as they are able. Subjects will also be asked to bring their lens case to the follow-up visit.

